### *Skin Assessments*

On the day of surgery, research staff obtained written HIPAA consent from participants and confirmed consent to participate in the study. Research staff collected visual skin assessment and sub-epidermal (SEM) measures for all participants at the anterior chin, upper cheeks, mid forehead (face), right and left upper chest above nipple line, and iliac crest, both pre-operatively in the Pre-Post Anesthesia Care Unit (PACU) and post-operatively in the PACU or after transfer to the floor unit. Once the pre-operative assessments were completed for intervention participants, research staff placed the multidimensionally flexible silicone foam (MFSF) dressings to the face (chin, cheeks, forehead), chest and iliac crest. Following surgery, research staff removed the MFSF dressings in the PACU or on transfer to the floor unit and then visual skin assessment and SEM measures were obtained. For all participants, visual skin assessments

and SEM measures were obtained daily on the floor unit until post-operative day five or discharge from hospital (whichever occurred first).

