device transmits high-frequency, low-power electromagnetic waves of 32 kHz via an electrode that requires light skin touch. In the skin, the induced electrical field interacts mainly with water molecules closest to the electrode, with depth of interaction depending on the diameter of the circular electrode (in this study depth was 4 mm). The portion of electromagnetic energy that is not absorbed by tissue water is reflected and measured by the device and displayed in three seconds in the measuring unit picoFarads (pF) (range, 0-7 pF). The electrical properties of free and bound water are nearly identical and thus the measure is reflective of total water content in the tissue.

*Definition Intraoperative Acquired PrIs.* Intraoperative acquired PrI (IAPrI) was defined two ways for each anatomic location. First, as erythema/skin discoloration of minimal or greater severity by visual skin assessment. Second, by calculating the difference between pre-operative and the post-operative SEM value (hereafter SEM Delta); SEM Deltas greater than or equal to 0.6pF were considered indicative of IAPrIs.

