### **Study Analysis Plan**

The two outcome measures, IAPrI incidence by visual assessment and SEM Deltas indicative of PrI, were compared between participants undergoing prone surgery with standard care (no dressings, pressure reduction positioning on the operating table) and those with standard care and the intervention (use of MFSF dressings placed on chest, iliac crest, and face). Using Fisher's Exact test statistics, the percent of participants with IAPrI on face, chest, and iliac crest as defined above were compared between the two groups for initial post-operative assessment and postoperative days 2 and 3 assessments. There were insufficient participants to evaluate postoperative days 4 and 5.

Using binary logistic regression analyses, demographic, medical and surgical factors were compared for prospective participants who did and did not develop skin damage or IAPrIs controlling for group. Factors that increase risk for IAPrIs were evaluated including: hospital length of stay, surgery length, body mass index (BMI), and skin tone. Cochran Mantel-Haenszel statistics were used to compare the groups.

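### The risk-factor regression gives its injury outcome no assessment window, although the number of skin checks depends on discharge; read as ever/never, it confounds injury risk with number of looks, most directly for hospital length of stay

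*Combined protocol and SAP*

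**What the plan says.** The second paragraph of the Study Analysis Plan describes a binary logistic regression comparing demographic, medical and surgical factors between "prospective participants who did and did not develop skin damage or IAPrIs controlling for group". The factors it evaluates for raised risk are "hospital length of stay, surgery length, body mass index (BMI), and skin tone". It does not say which assessment or assessments make a participant a case. It does not say whether the factors enter one joint model or separate ones. Group is the only control it names.

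Under Skin Assessments, visual checks and SEM measures follow surgery for everyone and then continue "daily on the floor unit until post-operative day five or discharge from hospital (whichever occurred first"). The number of checks therefore differs between participants. The plan confirms that numbers fell over time: "There were insufficient participants to evaluate postoperative days 4 and 5".

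The injury definitions do not supply a window. The visual one reads "First, as erythema/skin discoloration of minimal or greater severity by visual skin assessment", with no day attached. The SEM one is a rise of at least 0.6 pF from the pre-operative to the post-operative value, again without naming the day.

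The between-group Fisher tests, by contrast, are tied to named time points: "for initial post-operative assessment and postoperative days 2 and 3 assessments".

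**The concern.** The regression wording reads most naturally as ever/never: a participant counts as a case if any check was positive. Someone discharged early may have had one or two chances to be positive, and someone who stayed to day five had several more. Each further check is another opportunity to record minimal discoloration or a 0.6 pF rise. A yes/no model that controls only for group treats these unequal opportunities as equal.

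The factor most exposed is hospital length of stay, because stay largely sets the number of checks. Its odds ratio would exceed 1 even if stay had nothing to do with injury. An injury could also prolong the stay, which pushes the association the same way. Other factors that go with a longer stay can pick up part of this effect.

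At stake is the plan's aim of naming factors that increase IAPrI risk. A reader of the results could not tell how much of an odds ratio reflects injury and how much reflects looking more often.

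**Working it through.** The documents give no sample size, event rate or alpha, so there is no planned figure to reproduce. Everything below illustrates size under stated assumptions.

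**1. How many checks?** There is one initial post-operative check, then daily checks to day five at most. If the initial check falls before day 1, the maximum is six; if it counts as day 1, the maximum is five. The text does not settle this.

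**2. Effect on length of stay.** Assume every check has the same chance p of a positive, checks are independent, and no factor has any effect. Then P(ever positive after k checks) = 1 − (1 − p)^k. With p = 0.05:

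- k = 2: 1 − 0.95² = 0.0975, odds 0.0975/0.9025 = 0.1080
- k = 4: 1 − 0.95⁴ = 0.1855, odds 0.1855/0.8145 = 0.2277; odds ratio against k = 2 is 0.2277/0.1080 = 2.1
- k = 5: 1 − 0.95⁵ = 0.2262, odds 0.2262/0.7738 = 0.2924; odds ratio 2.7
- k = 6: 1 − 0.95⁶ = 0.2649, odds 0.2649/0.7351 = 0.3604; odds ratio 3.3

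Over a range of p:

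| p per check | 2 checks | 4 checks | 6 checks | OR 4 v 2 | OR 6 v 2 |
|---|---|---|---|---|---|
| 2% | 4.0% | 7.8% | 11.4% | 2.0 | 3.1 |
| 5% | 9.8% | 18.5% | 26.5% | 2.1 | 3.3 |
| 10% | 19.0% | 34.4% | 46.9% | 2.2 | 3.8 |
| 20% | 36.0% | 59.0% | 73.8% | 2.6 | 5.0 |

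Since the plan reports too few participants at days 4 and 5, the 4-versus-2 column is the more typical contrast. Independence is the extreme case. If a finding, once present or absent, never changed between checks, ever-positive would equal the first result and the distortion would vanish.

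**3. Effect on another factor with no true effect.** This was simulated with 1 to 6 checks per participant (assumed mean 2.9), a null factor with correlation ρ to stay, and p from 5% to 20%. Odds ratio per SD of the null factor when the outcome is ever positive and neither stay nor number of checks is in the model:

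| ρ | Independent checks | Strongly persistent findings (latent correlation 0.9) |
|---|---|---|
| 0.1 | 1.05–1.06 | 1.01–1.03 |
| 0.3 | 1.16–1.19 | 1.05–1.07 |
| 0.5 | 1.29–1.37 | 1.09–1.11 |

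With number of checks added to the model, the odds ratio returns to 0.99–1.02. With the initial assessment as outcome, it is 0.98–1.02.

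**4. False-positive rate at nominal 0.05** (p = 10%, independent checks, model with group only):

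- n = 100: 0.09 at ρ = 0.3, 0.19 at ρ = 0.5
- n = 200: 0.16 at ρ = 0.3, 0.38 at ρ = 0.5
- ρ = 0.1, either n: 0.04–0.07
- for ρ from 0.1 to 0.5 at these n, adding number of checks gives 0.04–0.05, and using the initial assessment only gives about 0.04–0.05

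**The case against.** The strongest reply is that the plan never says the outcome is pooled over follow-up. The injury is defined as acquired during surgery, the SEM definition refers to a single post-operative value, and the neighbouring Fisher tests use fixed time points. If the regression used the initial assessment, each participant has one scheduled look and this bias is zero. That stands. What the text establishes is an undefined window, and the detection bias is conditional on the ever/never reading.

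A reader might go further and infer that surgery length and BMI will look like risk factors whether or not stay is in the model. The documents do not support that. Length of stay is itself a listed factor, and if it enters jointly most of the bias in the other factors goes. At an assumed correlation of 0.6, putting stay rather than number of checks in the model left residual odds ratios of 1.04 to 1.13 under different simulation settings. The plan does not say the factors enter jointly, so this protection is possible but not assured. Joint modelling also does nothing for the length-of-stay estimate.

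A reader might also take large false-positive rates for surgery length as established. Rates of 21% to 42% can be produced (N = 100 to 150, 5% to 8% per check), but only with a correlation of 0.6 and independent checks. The documents give no correlation of surgery length or BMI with stay. Repeat looks at the same sites after one operation are also unlikely to be fully independent. With correlation 0.1 to 0.3 the rates are about 5% to 10% at sample sizes near 100, and with highly persistent findings about 5% to 7% even at 0.6.

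Finally, the between-group Fisher comparisons use fixed time points and are not touched by this mechanism. That also stands.

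**Conclusion.** The concern holds in a limited form. The regression outcome has no stated window, the number of checks is set by discharge, and only group is named as a control. If the outcome is ever/never, the odds ratio for hospital length of stay cannot be read as injury risk: with no true effect it would be about 2.1 for 4 against 2 checks and 3.3 for 6 against 2, assuming independent checks at 5% each, and lower if findings persist. Factors correlated with stay may carry a smaller bias when neither stay nor number of checks is in their model, ranging from negligible to about 1.37 per SD over assumed correlations of 0.1 to 0.5. That surgery length is such a factor is plausible but not documented; for BMI the documents offer nothing either way.

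It should be corrected because the remedy is cheap and the risk-factor results are otherwise uninterpretable on this point. It is a weakness of a secondary analysis and does not affect the fixed-time treatment comparison.

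**What to change.** State which assessment defines the regression outcome, and choose one of these:

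- **Initial post-operative assessment.** Every participant is scheduled to have it, so opportunity is equal. The cost is that late-appearing injuries drop out of this analysis.
- **All assessments.** Fit a discrete-time model (logistic or complementary log-log) with one record per participant per check, up to the first positive, and a term for assessment day. Participants contribute only the checks they had. This keeps late injuries, but assumes that discharge is unrelated to later injury given the covariates. As a minimum alternative, keep ever/never and adjust for number of checks.

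In either case, state whether the factors enter jointly or one at a time, and do not interpret hospital length of stay as a cause of IAPrI. It fixes the number of looks under an ever/never outcome, it may be a consequence of injury, and much of it falls after the initial assessment.

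The cost is a few sentences in the analysis plan and a re-run on data already collected.

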**Study Protocol and Study Analysis Plan**

## **Study Protocol**

### *Recruitment*

Patients from neurological and orthopedic surgery groups were recruited for the study at a 281-bed academic Medical Center in the greater Los Angeles area. Per approval by the University of California, Los Angeles, Office for Human Research Protection Program, research staff identified scheduled participants for surgery in the prone position, sent them an information sheet about the study, and then contacted them by phone to determine their interest in the study. Participants were eligible for the study if they were scheduled to undergo orthopedic or neurological surgery in prone position, 18 years of age or older, and able to provide verbal informed self-consent. Exclusion criteria were less than 18 years old, inability to provide verbal informed consent, and scheduled for surgery only in a position other than prone position.

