#### *Medical Record Data*

Research staff extracted medical, surgical, and demographic information was extracted from participants' electronic health records (EHR) using an investigator-developed abstraction tool. Data abstracted included demographic data (gender, age, race/ethnicity), medical data (height, weight, body mass index, comorbidities such as diabetes, hypertension, peripheral vascular disease and, smoking status, medical diagnoses, Braden Scale for predicting Pressure Sores (Braden) score, use of any PrI preventive strategies such as support surface use, repositioning schedules), surgery type, surgery length, use of vibration machines or other instruments in surgery, length of time in PAR unit, anesthesia used, use of vasopressors during surgery, estimated blood loss, volume of fluids provided during surgery, blood pressure during

surgery, American Society of Anesthesiologists physical status score and documentation of any skin damage. Using EHR data, a Scott-Triggers IAPrI risk assessment score was calculated for each participant. The Scott-Triggers tool examines four characteristics: age 62 years or older; albumin less than 3.5mg/dL or BMI less than 19 or greater than 40; American Society of Anesthesiologists physical status classification system (ASA) 3 or greater; and estimated surgery time over 3 hours. Each characteristic affirmed scores a point and scores greater than 1 indicate high risk for IAPrIs (37).

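### Hospital length of stay is evaluated as a factor that increases IAPrI risk, but it is not limited to days before surgery and ordinarily ends after the intraoperative injury

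*Combined protocol and SAP*

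**What the plan says.** The second paragraph of the Study Analysis Plan describes binary logistic regressions in which "demographic, medical and surgical factors were compared for prospective participants who did and did not develop skin damage or IAPrIs controlling for group". The next sentence names the factors: "Factors that increase risk for IAPrIs were evaluated including: hospital length of stay, surgery length, body mass index (BMI), and skin tone". The paragraph ends: "Cochran Mantel-Haenszel statistics were used to compare the groups". Nothing there or elsewhere gives a start or end point for hospital stay. No assessment time is given for the outcome of this analysis, although the Fisher comparisons in the preceding paragraph are tied to the initial post-operative assessment and to post-operative days 2 and 3.

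The Skin Assessments section labels the injury as acquired intraoperatively. One definition is visual. The other is obtained "by calculating the difference between pre-operative and the post-operative SEM value (hereafter SEM Delta"), with a threshold of 0.6 pF. The first post-operative check is in the PACU or after transfer to the floor. After that, visual assessments and "SEM measures were obtained daily on the floor unit until post-operative day five or discharge from hospital (whichever occurred first").

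Under Recruitment, "research staff identified scheduled participants for surgery in the prone position" and then contacted them by phone. Under Medical Record Data, the abstraction list includes surgery length and "use of vibration machines or other instruments in surgery, length of time in PAR unit, anesthesia used", but not hospital stay.

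**The concern.** A factor said to increase the risk of an injury has to be in place before the injury occurs. Surgery length, BMI and skin tone are all settled by the end of the operation. Hospital stay, as the term is normally used, is known only at discharge. Days in hospital before surgery would be a legitimate antecedent factor, but the plan does not say that this is what it means. Because participants were scheduled patients reached by phone, most of their stay probably followed surgery; that is an inference, not a documented fact.

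At stake is one conclusion of the risk-factor analysis. Followed as written, the plan could report that longer stay raises IAPrI risk, when total stay could at most be associated with IAPrI.

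**Working it through.** **1. Time order from the text.** The sequence is: pre-operative check, surgery (where the injury is by definition acquired), first post-operative check, daily checks to day five or discharge, then discharge. Total stay is complete only at the last step. The regression outcome is wider than IAPrI, since it also covers skin damage, and damage first seen on day 2 or 3 can follow days already spent in hospital. Total stay still counts days after that check, so it remains the wrong exposure. This holds whether stay was examined by logistic regression or by Cochran Mantel-Haenszel.

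**2. Size.** The plan gives no event rate, stay distribution or discharge delay, so there is no figure to reproduce and every input below is an assumption. Simulation of 400,000 patients (seed 1):

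- two groups, 1:1; surgery hours gamma with shape 9 and mean 4;
- logit P(IAPrI) = −1.4 + ln(1.5) × (hours − 4) + ln(0.5) × group, giving 16.6% IAPrI;
- stay = gamma (shape 4, mean 3.5 days) + b × (hours − 4) + d × IAPrI, with a floor of 0.2 day.

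Here b is days of stay added per surgery hour and d is days added by injury. Stay has no causal effect on injury in any row.

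| b | d | Logistic OR per day of stay, adjusted for group | Mantel-Haenszel OR, stay above v below median, stratified by group |
|---|---|---|---|
| 0 | 0 | 1.00 | 1.01 (simulation noise) |
| 0 | 0.5 | 1.165 | 1.66 |
| 0 | 1 | 1.33 | 2.91 |
| 0.5 | 0 | 1.11 | 1.42 |
| 1 | 0 | 1.16 | 1.78 |

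Rows two and three show a consequence of injury appearing as a cause. Rows four and five show a shared cause. In those last two rows, adding surgery length to the logistic model returns the stay OR to 1.00.

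The figures also move with the assumed stay distribution. With 20% IAPrI, gamma stay of mean 4 and SD 2 days and no covariates, delays of 0, 0.5 and 1 day give 1.00, 1.13 and 1.25 per day.

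**3. Number of checks.** This applies only if the outcome is a positive finding at any check. For an injury fixed at surgery with prevalence p and per-check sensitivity s, the chance of detection over m checks is p × [1 − (1 − s)^m]. With p = 0.2 and s = 0.5:

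- two checks: 0.2 × (1 − 0.25) = 0.150
- four checks: 0.2 × (1 − 0.0625) = 0.1875
- OR = (0.1875/0.8125) ÷ (0.150/0.850) = 1.31

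Over p = 0.1 to 0.3 the four-versus-two OR is 1.28–1.35 at s = 0.5, 1.04–1.06 at s = 0.8 and 1.00 at s = 1. It depends heavily on the contrast: at s = 0.5, three versus two checks gives 1.18–1.23 and three versus one gives 1.82–2.02.

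**The case against.** The strongest reply is that the documents never say total stay was analysed; pre-operative days would be legitimate, so the plan may only need a definition. This stands in part. A reader might infer that total stay was used, and the text does not establish that. But the ordinary sense of the term includes the days after surgery, and an analyst following the plan could use it without departing from it.

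A second reply is that the regression sentence only compares factors between those with and without injury, which is a valid descriptive association. That is true of that sentence. The next sentence describes the factors as increasing risk, and total stay cannot support that.

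Third, the sizes rest on mechanisms that the documents do not confirm. This stands. The shared-cause figures are confounding by surgery length, itself a listed factor, and they vanish when it is in the model; the plan does not say whether factors are modelled jointly. No passage shows that injury delays discharge, and the IAPrI definitions include minimal discoloration. The plan does not state an any-check outcome.

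Two further inferences should be resisted. Absence of stay from the Medical Record Data list does not show how it was measured, because skin tone is missing from that list too. And although that section says "The Scott-Triggers tool examines four characteristics: age 62 years or older; albumin less than 3.5mg/dL or BMI less than 19 or greater than 40" among its components, the plan never enters the Scott-Triggers score in the regression, so overlap between the score and its components is not a demonstrated problem.

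**Conclusion.** The point holds on time order, which needs no numerical assumption: a variable completed at discharge cannot be shown to increase the risk of an injury acquired during surgery. Which version of stay was used, and how large any bias would be, are both unknown. With no causal effect, the illustrative OR per day runs from 1.00 if injury adds no delay to about 1.33 if it adds one day, and the delay is an assumption.

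A reader might go further and infer that the treatment comparison is compromised. The documents do not support that, since the Fisher tests do not use stay. The problem is confined to one of four named factors in a secondary analysis. It should be corrected because the correction is cheap and the conclusion would otherwise be invalid.

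**What to change.** - Do not evaluate total hospital stay as an IAPrI risk factor, under either logistic regression or Cochran Mantel-Haenszel.
- If admission and surgery dates are available, days in hospital before surgery may be used instead, labelled as such. The Medical Record Data section does not list these dates, so availability has to be checked.
- Report total stay descriptively, or as an outcome by IAPrI status, with its start and end stated.
- Tie the risk-factor outcome to a fixed assessment: the initial post-operative check, with days 2 and 3 analysed separately, as in the Fisher tests. Stay then no longer sets the number of checks.
- The plan is written in the past tense. If the analysis was run with total stay, rerun it without that factor, disclose the change and describe the earlier result as an association only. Text stating that total stay was not evaluated as a risk factor would be true only after such a rerun.

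The cost is one listed factor, an edit to the text and a small rerun; removing stay needs no new data. The downside is that injuries first visible later are captured only in patients still in hospital on days 2 and 3.

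### The only dressing comparison with outcome, site and time point stated is an unadjusted Fisher test; the Cochran-Mantel-Haenszel analysis is left undefined and the Scott-Triggers score is named in no analysis

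*Combined protocol and SAP*

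**What the plan says.** The Study Analysis Plan names three methods.

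- **Fisher's exact test.** At the initial post-operative assessment and on days 2 and 3, "the percent of participants with IAPrI on face, chest, and iliac crest as defined above were compared between the two groups". No covariate or stratum is mentioned. The Skin Assessments section adds that IAPrI "was defined two ways for each anatomic location": by visual grade and by SEM Delta.
- **Binary logistic regression.** Here "demographic, medical and surgical factors were compared for prospective participants who did and did not develop skin damage or IAPrIs controlling for group". Group is a control term, and the stated target is the risk factors. The plan continues: "Factors that increase risk for IAPrIs were evaluated including: hospital length of stay", followed by surgery length, BMI and skin tone.
- **CMH.** The whole specification is "Cochran Mantel-Haenszel statistics were used to compare the groups".

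Under Medical Record Data, "a Scott-Triggers IAPrI risk assessment score was calculated for each participant", built from age, albumin or BMI, ASA class and estimated surgery time, and "scores greater than 1 indicate high risk for IAPrIs". The Study Analysis Plan does not name this score.

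**The concern.** CMH is a stratified method, so its stratifier largely decides what it estimates. Without one, the sentence cannot be reproduced, and a stratifier left unnamed can be picked once results are known. It is also unclear what was compared. It could be the arms within levels of a risk factor, or participants with and without IAPrI within arms.

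That leaves the unadjusted Fisher test as the only dressing comparison whose outcome, site and time point can be read from the plan. If allocation was random, the test is valid and adjustment matters little. If it was not, any difference in baseline risk between the arms passes straight into the Fisher result, and no stated analysis gives a baseline-adjusted dressing effect to set beside it. A plausible stratifier has already been calculated for every participant.

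**Working it through.** **Text check.** The CMH sentence is the only mention of the method.

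| Item | Fisher | Logistic | CMH |
|---|---|---|---|
| Groups compared | two arms | IAPrI yes/no, controlling for arm | not clear |
| Stratifier or covariate | none | factors listed | not stated |
| Site | three | not stated | not stated |
| Time point | three | not stated | not stated |

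With a single stratum, the CMH statistic is Pearson's chi-square multiplied by (N-1)/N. Without a stratifier it therefore adds nothing to an unadjusted comparison.

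**Inputs for the illustration.** The documents give no sample size, event rate or baseline imbalance, so there is no stated figure to reproduce. Assumed: IAPrI risk 10% in low-risk and 30% (or 40%) in high-risk participants; 50 or 100 per arm; two-sided 5% tests without continuity correction. Fisher and Pearson rejection rates come from exact enumeration of two binomials, CMH rates from 200,000 or more simulated trials per case.

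**Random allocation, within-stratum odds ratio 0.5, half of each arm high risk.** Dressing-arm risks follow from halving the odds: 10% becomes 5.3%, 30% becomes 17.6%, 40% becomes 25.0%. Overall rates are 20.0% against 11.5% (25.0% against 15.1%).

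| Per arm | CMH by score | Pearson | Fisher |
|---|---|---|---|
| 50 | 22.0% (25.0%) | 22.7% (23.8%) | 14.1% (16.7%) |
| 100 | 39.6% (45.0%) | 38.8% (42.0%) | 31.9% (34.9%) |

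Against Pearson, stratifying changes power by -0.7 to +3.0 points. Most of the gap between CMH and Fisher is Fisher's conservatism: its actual size with balanced arms is 2.8% to 3.4%.

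**Unequal baseline risk, no dressing effect.** Crude rate per arm = share high × risk high + (1 - share high) × 0.10. For 60% against 40% and risk 30%, this is 0.60 × 0.30 + 0.40 × 0.10 = 0.22 against 0.18. The odds ratio is (0.22/0.78)/(0.18/0.82) = 1.28. Odds ratios below are for the arm with more high-risk participants.

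| High-risk shares | Risk in high-risk | Crude rates | Crude OR | Fisher rejects, 50 / 100 per arm | OR stratified by imperfect score |
|---|---|---|---|---|---|
| 60% v 40% | 30% | 0.220 v 0.180 | 1.28 | 4.8% / 7.9% | 1.18 |
| 65% v 35% | 30% | 0.230 v 0.170 | 1.46 | 7.5% / 14.2% | 1.29 |
| 60% v 40% | 40% | 0.280 v 0.220 | 1.38 | 7.2% / 12.7% | 1.24 |
| 65% v 35% | 40% | 0.295 v 0.205 | 1.62 | 12.9% / 25.7% | 1.39 |

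The last column assumes that the score classifies true risk with 80% sensitivity and specificity, independently of arm and outcome. First row, as fractions of each arm: the score-high stratum holds 0.56 (0.152 with IAPrI) against 0.44 (0.108), and the score-low stratum 0.44 (0.068) against 0.56 (0.072). The two arms' fractions sum to 1 in each stratum, so

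OR = (0.152 × 0.332 + 0.068 × 0.488) / (0.108 × 0.408 + 0.072 × 0.372) = 0.08365 / 0.07085 = 1.18.

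If the score captured the whole imbalance, CMH would reject about 5% of the time by construction. With the 80% score it rejects 6.1% to 10.5% at 50 per arm and 7.4% to 16.4% at 100. At 100 this is below Fisher in all four rows. At 50 it is at or above Fisher in three of four, two of them near ties. With 70% sensitivity and specificity the odds ratio stays at 1.24 to 1.52.

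**Sparse events.** With risks of 3% and 10%, the Mantel-Haenszel odds ratio is undefined in about 7% to 20% of trials at 50 per arm and 0.2% to 3.3% at 100. With 10% and 30% the figure is at most 0.2% at 50.

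**The case against.** The strongest reply is that this is a reporting gap. The CMH sentence closes the risk-factor paragraph, so its groups could be participants with and without IAPrI, with arm as stratifier, which is a standard use. A reader might infer that a stratified arm comparison was intended and left unspecified; the text does not settle that. The general reference to demographic, medical and surgical factors could also cover the Scott-Triggers score without naming it. Both points stand, and they are why the first step is to report what was done.

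Second, choosing Scott-Triggers now is itself a choice made late. The plan is in the past tense and reports too few participants for days 4 and 5, so data had been examined. This also stands. It rules out replacing the CMH analysis that was run, or promoting the new estimate to the main one.

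Third, every magnitude is assumed, and in small arms an imperfect score may not lower the false-positive rate. At 20, 25 and 30 per arm CMH rejected more often than Fisher in all twelve cases (5.2% to 8.2% against 2.9% to 7.6%). Fisher's conservatism contributes to this, but it means that the case for adjustment rests on the estimate and its interval, not on another p-value.

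Fourth, the abstraction list includes surgery length but neither albumin nor estimated surgery time, so whether the score is purely pre-operative needs confirming.

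What the reply does not remove is that no stated analysis yields a baseline-adjusted dressing effect, although a suitable score is already in the data.

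**Conclusion.** The point holds in a limited form. The CMH analysis cannot be reconstructed, the one dressing comparison with outcome, site and time point stated is unadjusted, and no analysis names the Scott-Triggers score. A change is worth making because it is cheap and gives an adjusted estimate with an interval.

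Four stronger readings are tempting and are not supported:

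- **That the dressing comparison is biased, or allocation was not random.** The available text shows neither, and the document's opening material may describe allocation.
- **That the Fisher test is fully specified.** Alpha, sidedness and the rule for combining the four face locations or the paired chest and iliac locations are not given.
- **That adjusting for length of stay spoils the group coefficient of the logistic model.** This assumes one joint model; the factors may have been examined one at a time, each controlling for group.
- **That stratifying by the score would remove confounding.** On the assumed inputs a crude odds ratio of 1.28 to 1.62 falls only to 1.18 to 1.39 with an 80% accurate score.

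Under random allocation the effect on power is about -1 to +3 points. Any larger consequence needs non-random allocation and a real imbalance, neither of which is known.

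**What to change.** 1. State which groups, stratifier, outcome definition, site and time point the CMH analysis actually used. Do not replace it.
2. Beside each Fisher result at the initial post-operative assessment, report a Mantel-Haenszel odds ratio with 95% CI for dressing against standard care, stratified by Scott-Triggers above 1 against 1 or less. This gives 3 sites × 2 definitions = 6 estimates. Where events are too few, give the exact conditional common odds ratio and its CI.
3. Confirm that the score uses pre-operative information only. Do not adjust the dressing effect for post-operative variables such as length of stay.
4. Keep to the initial assessment. Daily assessments end at discharge, so days 2 and 3 cover only those still in hospital, and a baseline stratifier does not repair that selection.
5. Present these as supporting estimates, labelled post hoc if the data were already analysed. If allocation was not random, do not interpret the Fisher results without them, and say that the adjustment is only partial.

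The cost is six further estimates on data already abstracted, probably post hoc. They should not be read as six more tests. Confounding that the score does not capture remains.
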